2.2 Background

Postoperative pain following total knee arthroplasty is a substantial medical problem
Total knee arthroplasty (TKA, i.e., total knee replacement) is a surgical treatment for painful and debilitating knee conditions, such as osteoarthritis (OA), which affects 5% of adults (9-18 million people) (Murphy & Helmick 2012, Neogi & Zhang 2013, London et al. 2011). In the U.S., approximately 719,000 TKA procedures were performed in 2010 (CDC, 2010), and this number is expected to grow to 3.5 million procedures per year by 2030 (Kurtz et al. 2007).

The first 4 weeks following TKA surgery are a critical period for physical rehabilitation, which is essential for functional recovery following TKA. Adequate levels of quadriceps strength and knee range of motion are required for activities of daily living (Jones et al. 2003). However, during the first 4 weeks, quadriceps strength is diminished substantially by 48-60% (Bade et al. 2010, Bade & Stevens 2011, Mizner et al. 2005), and knee range of motion is diminished (Su et al. 2010).

Patients that can undergo early and intense rehabilitation can minimize the loss of quadriceps strength and prevent knee stiffness (*i.e.*, reduced range of motion), resulting in greater long-term functional outcomes exceeding preoperative levels (Shoji et al 1990, Bade & Stevens 2011). However, the start of physical rehabilitation and the intensity and duration of rehabilitation are limited by both existing pain and the fear of inducing additional pain (Ryu et al. 1993, Bade & Stevens 2011). This delay and reduced intensity of therapy often impedes recovery, and up to 27% of patients (up to 194,000 new cases/year) have not achieved full functional recovery ≥ 1 year following surgery (Jones et al. 2003, Singh et al. 2010).

Approximately half (30-90%) (Andersen et al. 2009, Dahlen et al. 2006, Strassels et al. 2004, Choy et al. 2011, Brander et al 2003) of all TKA patients experience moderate to severe pain during the first month after TKA surgery that can interfere with rehabilitation during this critical period, resulting in impaired function for several months following TKA. Over half of TKA patients (52%) are unable to walk 30 minutes without severe pain at 6 months after TKA, and 17% have severe pain while walking any distance at 1 year after TKA (Dawson et al. 1998). Also, walking speed at 1 year after TKA is 18% slower overall and 51% slower on stairs compared to individuals with healthy knees (Walsh et al. 1998), and 60-80% of TKA patients experience difficulty climbing stairs several months to years after TKA (Jones et al. 2003, Bade & Stevens 2011, Walsh et al. 1998). In addition, 64-84% of patients have difficulty with other activities of daily living $\geq 6-12$ months following TKA, (*e.g.*, work, getting in/out of a car, shopping) (Jones et al. 2003, Walsh et al. 1998) and this severely limits independence and quality of life. In addition to interfering with rehabilitation, postoperative pain can become chronic pain if uncontrolled, (Capdevila et al. 1999, Peters et al. 2007, Puolakka et al. 2010, Sinatra 2010) which is moderate to severe in up to 35% of patients (Brander et al. 2003, Visser 2006, Callahan et al. 1994, Wylde et al. 2011, Peng et al. 2014).

Present treatments for postoperative TKA pain are ineffective, carry risks of side effects/complications, and/or are not indicated for extended use.

Following TKA, patients are given various treatments to relieve postoperative pain. The most common treatment strategy is multimodal pain management, consisting of various medications (analgesics) used in combination with regional nerve blocks.

Analgesics: Although analgesics are used both in-hospital and in the home environment after discharge, their risks of side effects and dependence make them undesirable. The primary analgesics used in multimodal pain therapy are opioids (*e.g.*, oxycontin), which carry risks of dependence and debilitating side effects that cause substantial discomfort and interfere with physical rehabilitation (*e.g.*, sedation, dizziness, nausea, gastrointestinal problems, sleeping problems) (Sinatra 2010, Strassels et al. 2005, Apfelbaum et al. 2003, Wheeler et al. 2002, Kastanias et al. 2010, Benyamin et al. 2008, Eisenberg et al. 2005). Anticonvulsants (*e.g.*, gabapentin, pregabalin) are also used in multimodal pain therapy (Andersen et al. 2009, Buvanendran et al. 2010, Clarke et al 2009) but also carry risks of side effects (sedation, dizziness, headache, blurred vision) that limit physical rehabilitation (Buvanendran et al. 2010, Clarke et al 2009, Zhang et al. 2011). Other non-opiates (NSAIDs, acetaminophen) have minimal risk of side effects but are insufficient on their own and are most often paired with other analgesics. Fear of pain medications and addiction is one of the top concerns of patients prior to TKA (Chang et al.

2004).

Regional nerve blocks: Single shot (*i.e.*, injection) and continuous blocks (*i.e.*, using a catheter) can provide relief of postoperative pain while recovering from surgery in the hospital, but they are not suitable for extended use outside the hospital. Blocks targeting mixed nerve trunks (*i.e.*, femoral, sciatic, “3-in-1”) can inhibit motor function in the lower limbs, impeding physical rehabilitation and increasing the risk of falls. Alternative approaches can avoid motor block (*i.e.*, adductor canal block, periarticular/intraarticular block) and are useful in-hospital but cannot be practically or safely delivered in the home environment. The analgesic effects of injections last for ≤ 48 hours and cannot be delivered outside the clinical setting. Continuous nerve blocks are seldom used for more than 7 days due to the risk of infection from indwelling catheters.

Single injections (intrarticular injections of the knee, or injections of the femoral nerve, sciatic nerves, and/or their branches) are short lasting (2 – 48 hours), and can lead to block of normal motor and/or sensory function. It is often challenging to administer adequate anesthesia that provides a sufficient sensory block without impairment of muscle function. If motor/sensory block occurs, then rehabilitation is typically delayed until the effects wear off since the patient is at greater risk of falling. Epidural anesthesia can be used to relieve postoperative pain but carries risks of various side effects: epidural bleeding, diminished muscle control, urinary retention, nerve damage, gluteal compartment syndrome, spinal headache, neurogenic bladder, hypotension, respiratory depression, pulmonary hypertension, cardiac decompensation, and risk of spinal infection (Busch *et al.* 2006; Vendittoli *et al.* 2006). Continuous nerve block of the femoral nerve, sciatic nerves, and/or their branches is a treatment where a catheter is placed percutaneously and delivers anesthetic continuously to the peripheral nerves. Although this treatment can reduce acute postoperative pain, there are several risks that limit its use. The risk of infection is a great concern for any TKA treatment but particularly during continuous nerve block. A previous study reported that after 48 hours of Continuous Femoral Nerve Block, 118 (57%) of 208 catheters had positive bacterial colonization. Only 3 of the 118 incidents of colonization (2.5%) resulted in infection (fever, bacteremia), which resolved with removal of the catheter and without antibiotics (Cuvillon *et al.* 2001). However, the rate of infection likely would have been higher had the catheters been left in for longer than 48 hours. Another risk of continuous nerve blocks is impaired motor and sensory function. Because of the concern that nerve block may cause falls during rehabilitation, and rehabilitation is essential to the recovery of normal functioning, continuous nerve blocks are discontinued after a few days to enable the patient to move about. However, pain intensity is greater during movement than during rest (Singelyn *et al.* 1998; Reuben *et al.* 2008; Andersen *et al.* 2009; Fu *et al.* 2009; Lee *et al.* 2011), leaving patients without this option.

Transcutaneous electrical nerve stimulation (TENS): TENS has been investigated as a method of relieving postoperative pain. Although TENS is a widely accepted method of relieving chronic pain, there is limited evidence that it is effective at relieving postoperative pain. When delivered at a sufficient frequency and amplitude, TENS has reduced postoperative pain (Bjordal *et al.* 2003). However, stimulation intensity during TENS is often limited due to the activation of cutaneous nerve fibers, which can cause discomfort and irritation. Because stimulation intensity is limited during TENS, the therapy delivered may be suboptimal.

The proposed non-narcotic therapy may reduce postoperative pain with minimal risk of infection and falls

The proposed method aims to relieve postoperative pain following TKA by delivering electrical stimulation through percutaneous fine wire Smartpatch MicroLeads connected to an external pulse generator to target the [REDACTED] nerves. Unlike TENS, the leads are placed [REDACTED]

[REDACTED] and can stimulate the target nerves without cutaneous discomfort.

[REDACTED] Also, compared to the catheters used in continuous nerve blocks, data suggests that the leads pose less of a risk of infection. Also, previous studies indicate that [REDACTED] are not expected to impair motor and sensory function (see Section 11), which may enable the patient to achieve rehabilitation goals sooner and with less pain.

The proposed therapy may provide immediate pain relief following TKA that can be delivered for several weeks as patients continue their postsurgical recovery

The proposed method may provide immediate pain relief as soon as stimulation is started. PNS also allows for consistent pain relief as stimulation can be provided up to 24 hours per day. Conversely, standard of care treatments typically have a pre-set duration in which pain relief lasts before another dose or therapy must be initiated. The proposed method also will provide stimulation for up to 8 weeks post lead placement, allowing patients access to non-narcotic pain relief throughout their hospitalization, discharge, and rehabilitation.

The proposed method has been successfully used to [REDACTED]

[REDACTED] **reduce chronic pain in patients with lower limb amputations**

The proposed method to treat postoperative pain following TKA has been tested as a treatment for chronic pain in individuals with lower limb amputations.

[REDACTED]

The proposed method has been tested to treat pain in patients following TKA in a separate preliminary study.

Three subjects with pain following TKA (range: postoperative day 6-9) were tested with the proposed approach in a non-significant risk case series study.

Summary

Postoperative pain is a substantial problem for a majority of patients following total knee arthroplasty. Present treatments for postoperative pain during the subacute phase (4 – 30 days following surgery) are ineffective, carry risks of side effects/complications, and/or are not indicated for extended use. The proposed therapy using percutaneous electrical stimulation

is expected to reduce postoperative pain and address the shortcomings of existing therapies. The proposed study will determine if this therapy can produce clinically significant reductions in postoperative pain following TKA as compared to historical controls (e.g., published data).

3.0 STUDY OUTCOMES AND EXPLORATORY MEASURES

3.1 Overview

Outcomes and exploratory measures will be collected before and after TKA surgery (see Appendix A for schedule) and include

1. Numerical rating scales for pain intensity: Average Pain while walking (Question 5 of the Brief Pain Inventory-Short Form; BPI-5)
2. Numerical rating scales for pain intensity: Average Pain and Average Pain at rest (Question 5 of the Brief Pain Inventory-Short Form; BPI-5)
3. Cumulative analgesic usage
4. Opioid related side effects (e.g., nausea and vomiting, constipation, urinary retention, pruritis, drowsiness, respiratory depression)
5. Range of Motion (knee flexion and extension angle)
 - a. Number of days to achieve key milestones in affected knee (e.g., 90 degree flexion)
 - b. Pain “right now” scores before, during, and after ROM testing
6. Timed Up and Go (TUG) test
7. Six Minute Walk Test
8. Fixed Distance Walk Test
9. Western Ontario and McMaster Universities Osteoarthritis Index (WOMAC)
10. Numerical rating scales for pain intensity: Pain Interference (Question 9 of the Brief Pain Inventory-Short Form; BPI-9)
11. Patient Global Impression of Change (PGIC)
12. Pain Catastrophizing Scale (PCS)
13. Time to meet recovery milestones
14. Subject satisfaction survey
15. Subject-shaded diagrams of pain and paresthesia
16. Clinician satisfaction survey

3.2 Primary Outcome

The primary outcome of this study will be the average daily pain while walking over the first 4 weeks following TKA surgery. This will be recorded using Question 5 of the Brief Pain Inventory Short Form (BPI-5; details of BPI below), which assesses “Average Pain” on an 11 point numerical rating scale, with one end representing “No pain” (0) and the other end representing “Pain as bad as you can imagine” (10). Subjects will record BPI-5 scores daily in a diary, and the mean score over the first 4 weeks following TKA will be calculated for each subject. The primary outcome will be compared to historical controls (e.g., published data).

3.3 Secondary Outcomes

Secondary outcome measures will provide additional information on pain and function, which will be used to aid in the design of future clinical studies.

Brief Pain Inventory-Short Form (BPI)

The BPI is a widely used assessment designed to measure pain intensity and the interference of pain on daily activities and moods (Cleeland and Ryan 1994). The BPI is recommended by the Initiative on Methods, Measurement, and Pain Assessment in Clinical Trials (IMMPACT) panel and has demonstrated validity and reliability across many cultures and languages (Cleeland and

Ryan 1994; Tan et al. 2004; Dworkin et al. 2005). The IMMPACT panel was assembled to develop consensus recommendations to improve and standardize the design and conduct of clinical trials involving treatments for pain.

Cumulative Analgesic usage

The amount and type of analgesic used by the subject will be recorded daily in a diary before TKA surgery, from the subject's records during their hospital stay, in daily diaries after discharge from the hospital, and at each visit following End of Treatment. Specific analgesic information that will be collected may include Patient Controlled Analgesia (PCA) dosage requests, PCA dosage, intravenous (IV) medications (opioids and non-opioids), oral opioids, and oral non-opioid pain medications. This information will provide an indirect measure of pain intensity, as usage of analgesics may relate to the amount of pain experienced. Narcotic usage may be converted into a morphine equivalent dosage (MED). The use of other methods of pain relief will also be recorded (e.g., cryotherapy).

Opioid Related Side Effects

Opioid pain medications are associated with a wide variety of side effects. Common side effects include nausea and vomiting, constipation, urinary retention, pruritis, drowsiness, and respiratory depression. Subjects may be questioned for each of these side effects throughout the study. Side effects from narcotic therapy will be collected but not reported as adverse events.

Range of motion

Adequate knee ROM is essential for activities of daily living but is limited by postoperative pain.. The active ROM (AROM; no assistance from clinical staff) and passive ROM (PROM; assisted by clinical staff) will be assessed during the study, and when possible the same clinical staff members at each site should take all ROM measurements to limit intertester variability.

Pain may be assessed before, during, and/or after ROM measurements (e.g., at maximum flexion, at maximum extension) using Question 6 of the Brief Pain Inventory-Short Form (BPI-6). BPI-6 rates “Pain right now” on an 11 point numerical rating scale, with one end representing “No pain” (0) and the other end representing “Pain as bad as you can imagine” (10).

Timed Up and Go (TUG) Test

The TUG test is an objective measure of mobility. The subject begins by sitting in a standard chair (e.g., uncushioned chair with armrests and seat height of 46 cm). A line is placed on the floor approximately ten feet (i.e., 3 meters) away. The subject is timed while they stand up, walk to the line at a normal, safe pace, walk back to the chair, and sit down. The test is reliable, a good indicator of the patient’s recovery from TKA, and easy to complete. The TUG test will be completed at various time points, including: the baseline visit (Visit 1), once during the in-hospital treatment visits, such as the anticipated last visit before discharge (when deemed safe by clinical staff), and during visits following hospital discharge. Regular footwear should be worn, and the use of any assistive devices (e.g., canes, walkers) is permitted and will be recorded.

Six minute walk test (6MWT)

The 6MWT records the total distance the subject can walk in 6 minutes. It is frequently used to measure endurance and is validated as a measure of mobility following TKA. Assistive devices (e.g., canes, walkers) may be used during the 6MWT. If the 6MWT can be conducted, then the total distance walked is recorded (subjects unable to walk at all will receive a score of 0 meters). Subjects will be allowed to rest during the test if necessary. The 6MWT may be administered at Visit 1 (before TKA surgery) and at visits following hospital discharge.

Fixed distance walking test

Subjects may be asked to walk a fixed distance (e.g., 20 meters) with or without an assistive device or help from clinical staff, and the time required to walk this distance may be measured to assess walking speed. Also, the first day following TKA surgery at which the subject can walk specific distances (e.g., 20 meters) may be recorded. The test may be administered at Visit 1 and once during the in-hospital treatment visits, such as the anticipated last visit before discharge (when deemed safe by clinical staff).

Western Ontario and McMaster Universities Osteoarthritis Index (WOMAC)

The WOMAC is a widely-used validated questionnaire to evaluate patients with osteoarthritis of the knee and consists of 24 items evaluating pain (5 items), stiffness (2 items), and physical functional disability (17 items) (Bellamy *et al.* 1988). Each item is scored on an 11 point numerical rating scale from 0-10, and greater scores indicate worse pain, stiffness, and functional disability. The WOMAC may be administered at Visit 1, during in-hospital visits, and during visits following hospital discharge. Also, WOMAC scores from before the TKA procedure may be collected from medical charts, if available.

Patient Global Impression of Change (PGIC)

Participant ratings of global improvement are one of the core outcome domains in chronic pain studies (Dworkin *et al.* 2005). The Patient Global Impression of Change (PGIC) Scale will be administered during in-hospital treatment visits and at visits following hospital discharge to assess subject perception of overall improvement (Guy 1976). The PGIC Scale asks subjects to rate their improvement with treatment on a 7-point scale that ranges from “very much worse” to “very much improved”. The scale provides subjects the opportunity to combine all of the components of their experience into one overall measure and allows clinicians to assess the clinical significance of each subject’s improvement or worsening over the course of the study.

Pain Catastrophizing Scale (PCS)

The PCS is a widely-used, validated and reliable 13-question instrument to assess rumination (4 questions), magnification (3 questions), and helplessness (6 questions) (Sullivan, 2009.; Osman *et al.* 1997). The survey asks participants to think back on painful experiences in the past and reflect on how often they had specific thoughts or feelings. Each question is scored on a 0-4 scale with 0 = “not at all” and 4 = “all the time”. Higher scores indicate a greater tendency towards catastrophizing pain, which has been correlated with worse postoperative pain and response to pain therapies (Riddle *et al* 2010; Pavlin *et al* 2005; Forsythe *et al* 2008). The PCS may be assessed at Visit, 1 the EOT visit and at the three-month follow-up visit.

Time to Meet Recovery Milestones

Discharge criteria differ between hospitals, but may include the following: 1) patient is medically stable, 2) pain controlled without nerve block (*i.e.*, single shot or continuous regional/neuraxial nerve blocks), 3) patient able to walk 30 meters ensuring Activities of Daily Living can be completed at home, and 4) patient can walk a set number of stairs (e.g., half a flight). The time until the subject meets criteria related to hospital discharge will be measured. Also, the subject’s length of stay in the hospital following TKA will be recorded (number of days and/or hours), as well as discharge destination (*e.g.*, home, acute inpatient rehabilitation, skilled nursing facility). In

addition, the time required to reach other important recovery milestones may be measured, such as 1) walking with assistive device (e.g., cane, quad stick, walker), 2) walking without assistive device, 3) return to work, and 4) cessation of narcotic usage.

Subject satisfaction survey

A survey will be administered to the subjects at study intervals to assess their satisfaction with the study and postsurgical pain therapies.

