5.2 NUMBER OF SUBJECTS

Up to 36 subjects will be enrolled in the study. Enrolled subjects are those that undergo procedures associated with lead placement. All enrolled subjects will receive a Subject ID number. The number of subjects to be enrolled does not include subjects who do not meet all of the eligibility criteria or who do not undergo procedures associated with lead placement.

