6.3.2 Exclusion Criteria

1. Body Mass Index (BMI) > 40 kg/m²
2. Compromised immune system based on medical history
3. History of valvular heart disease
4. Implanted cardiac pacemaker/defibrillator or Deep Brain Stimulator
5. Evidence of joint or overlying skin infection of the affected limb

6. History of recurrent skin infections
7. Bleeding disorder **OR** INR ≥ 1.5 for those on warfarin

Confounding conditions [REDACTED]

[REDACTED] History of nerve damage in the affected lower limb [REDACTED]

10. Allergy to skin surface electrodes and/or medical-grade adhesive tapes
11. Allergy to all local anesthetic agents such as lidocaine or previous reaction to anesthesia
12. Any other medical condition that may interfere with ability to participate in a clinical trial as determined by the Investigator
13. Prisoners, minors, legally incompetent people, unconscious patients, house staff, or students
14. Pregnant
15. History of substance abuse within 6 months

[REDACTED] Potential secondary gain issues [REDACTED]

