6.5.1 Visit 1 - Consent

Subjects will receive a detailed explanation of study specific procedures as well as the risks and benefits of participating in the study. The subject will be asked to sign the approved study consent during this visit. If the subject agrees to participate by signing the consent form, all inclusion/exclusion criteria will be verified by completing the eligibility form and then all baseline information will be collected and recorded on the appropriate case report form (CRF).

The subject's most recent pre-operative measurements of Range of Motion (ROM) may be documented, if available. The following outcome measures may be assessed:

- BPI-5 (“Average pain”) standard, at rest, and while walking
- Fixed Distance Walk test
- TUG test
- Six Minute Walk test
- BPI-9 (Pain Interference)
- WOMAC
- Pain Catastrophizing Scale (PCS)
- Current pain treatments and analgesic usage
- Assessment for opioid related side effects

[figure not shown]
If needed due to time constraints, any of the above outcome measures may instead be performed at Visit 2. Women of childbearing age will have a pregnancy test completed as part of eligibility confirmation before or at Visit 2.

[figure not shown]
[figure not shown]

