8.1 Analysis of Outcomes and Exploratory Measures

A table of outcomes and exploratory measures to be collected during the study can be found in Appendix A.

Question 5 of the Brief Pain Inventory-Short Form (BPI-5) is an 11-point numerical rating scale rating “Average Pain”. The BPI-5 will be measured at Visit 1 to establish a baseline score, as well as daily during stimulation and monthly post-EOT. For each subject, the mean over the first 4 weeks following TKA surgery will be calculated. An overall mean across all subjects for the first 4 weeks following TKA surgery will be calculated as well. This outcome will also be compared to historical controls (e.g., published data).

Additionally, sub-analyses will be performed to determine the mean over different post-operative phases (such as acute (e.g., days 1-7) or subacute (e.g., days 7-28)); calculate the mean for each subject and across subjects up to End of Treatment (week 6); and evaluate the proportion of subjects with pain below a certain threshold (e.g., 4/10).

Subjects will also rank their daily “Average Pain” (BPI-5) while walking. These data will undergo the same analysis as listed above for the standard BPI-5. This outcome will also be compared to historical controls (e.g., published data).

At the weekly visits during stimulation, subjects will be asked to report their weekly “Average Pain” (BPI-5) while at rest. The mean over different intervals (such as weeks 1-4 or weeks 1-6) will be calculated.

At each study visit, pain treatments and analgesic usage will be recorded. Changes in analgesic usage will be calculated using morphine equivalent dosing (MED). The usage of analgesics over various intervals (such as weekly averages, during weeks 1-4, etc.) will be calculated.

Medication usage will also be compared to pain scores to examine the correlation between analgesic usage and pain. The time to cessation of opioid will be determined. Also at each study visit, subjects will be queried for opioid related side effects. The number of effects noted over various intervals will be calculated.

Range of motion [REDACTED] will be collected at visits before, during, and after treatment. The time to achieve milestones (e.g., 90 degrees flexion, 100 degrees flexion) will be calculated for each subject and across all subjects. The mean flexion, extension, and range of motion (flexion – extension) across all subjects will be determined. The same will be calculated for passive ROM and active ROM.

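### Section 8.1 summarises opioid usage, time to opioid cessation and opioid side effects without using the pre-operative opioid and symptom status that the protocol schedules

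*Combined protocol and SAP*

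**What the plan says.** **Collection before surgery.** Section 3.3 (Cumulative Analgesic usage) states: "The amount and type of analgesic used by the subject will be recorded daily in a diary before TKA surgery". Section 6.5.1 lists "Current pain treatments and analgesic usage" and "Assessment for opioid related side effects" among the Visit 1 measures. Section 6.5.2 lists the same two items at Visit 2, before lead placement, and Appendix A marks both visits.

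**Who can enrol.** The nearest readable exclusion in section 6.3.2 is "History of substance abuse within 6 months". Section 6.4 permits opioids as prescribed.

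**Analysis.** Section 8.1 calculates analgesic usage over various intervals. On cessation it says "The time to cessation of opioid will be determined". On side effects it says "The number of effects noted over various intervals will be calculated". Section 3.3 also lists "cessation of narcotic usage" as a recovery milestone, and section 8.1 reports a mean number of days for each milestone. One further sentence provides for changes in analgesic usage in morphine equivalents (MED), without saying relative to what. The only subject grouping named in section 8.0 is by site or surgeon.

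**The concern.** Section 3.3 justifies recording analgesic use as an indirect measure of pain. For a subject who simply continues a pre-operative opioid regimen, the postoperative total measures that regimen as well as postoperative need. Such a subject may also never reach a cessation date, whatever the quality of postoperative pain control. A symptom such as constipation that was present at Visit 1 can enter the postoperative side-effect count.

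The stake is interpretation. Section 3.3 says that the secondary outcomes will help to design later studies, and section 2.1 rests the case for the therapy on the need for a non-opioid treatment, so the opioid results will be read closely. Opioid side effects are not reported as adverse events (sections 3.3 and 10.0), so the count in section 8.1 is their only planned summary.

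**Working it through.** The plan gives no opioid-use rate, dose, SD or sample-size calculation, so it has no figure to reproduce. The check is mainly one of text; the arithmetic only illustrates scale.

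**Step 1: does any sentence in section 8.1 use pre-operative status?**
- Usage over intervals: no. The sentence on change in usage may do so, but names no reference period.
- Time to cessation: no. There is also no rule for a subject still using opioids at the last visit. Dropping such subjects from a mean leaves out the longest users; entering their last follow-up day understates their time.
- Side effects: no. Effects are counted over intervals, with no rule for symptoms already present.
- By contrast, section 8.1 does specify postoperative minus pre-operative differences for WOMAC and BPI-9.

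**Step 2: is the pre-operative status certain to exist?** Not fully. Section 3.3 says usage will be diarised daily before surgery. Section 6.5.2 makes the pre-operative diary optional and ties it to subjects who receive pre-operative stimulation. The Visit 1 and 2 items are measures that *may* be assessed. Section 6.5.4 allows Visits 1, 2 and 4 on one day. A yes/no record of prior use is realistic; an individual daily level may not always be.

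**Step 3: illustration.** From the documents: "Up to 36 subjects will be enrolled in the study", and a four-week interval (28 days). Everything else is assumed.

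*Usage, relative scale.* With p the share of prior users and k the ratio of their mean usage to that of non-users, pooled mean / non-user mean = 1 + p(k − 1):

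| p | k = 1 | k = 1.5 | k = 2 | k = 3 |
|---|---|---|---|---|
| 0.1 | 1.00 | 1.05 | 1.10 | 1.20 |
| 0.2 | 1.00 | 1.10 | 1.20 | 1.40 |
| 0.3 | 1.00 | 1.15 | 1.30 | 1.60 |
| 0.4 | 1.00 | 1.20 | 1.40 | 1.80 |

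*Usage, mg scale.* Suppose a prior user continues unchanged at 20 or 40 mg MED/day. Over 28 days: 28 × 20 = 560 mg or 28 × 40 = 1,120 mg. At 25% prior users this adds 0.25 × 560 = 140 mg or 0.25 × 1,120 = 280 mg to the group mean. Moving from 15% to 35% prior users shifts the mean by 0.20 × 560 = 112 mg or 0.20 × 1,120 = 224 mg with no change in postoperative need.

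*Chance case mix.* If the true share is 0.30, the 2.5% and 97.5% binomial quantiles for 36 subjects are 6 and 16. With k = 2 the ratio would then run from 1 + 6/36 = 1.17 to 1 + 16/36 = 1.44 by enrolment chance alone.

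*Side effects.* With q the share who have a symptom before surgery (assumed to persist) and r the onset rate among the rest, pooled prevalence = q + (1 − q)r. At r = 0.30: q = 0.1 gives 0.1 + 0.9 × 0.30 = 0.37; q = 0.4 gives 0.4 + 0.6 × 0.30 = 0.58.

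*Precision after a split.* The 95% half-width for a mean, t(0.975, n − 1)/√n in SD units, is 0.34 for n = 36, 0.41 for 25 non-users and 0.67 for 11 prior users (p = 0.3).

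**The case against.** **Pooling is not stated.** A reader might infer that section 8.1 prescribes a pooled analysis of all three outcomes. It does not say so; it is silent on any split. This objection stands as to wording. The milestone sentence, with its mean days to each milestone, is the closest to explicit pooling, and it covers cessation only. Silence still leaves the handling of prior users to be chosen after the data are seen.

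**Change in usage may already be change from baseline.** That is a natural reading, since use before surgery is recorded, and it would partly deal with usage. It does not reach cessation or side-effect counts.

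**Pre-operative and postoperative side-effect counts could be compared by interval.** They could, but group counts do not show which postoperative effects were new in a given subject.

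**The SD for later planning.** A reader might infer that a pooled SD is inflated and would mislead a later sample-size calculation. The documents do not support this. If a later trial enrols the same mix and analyses raw usage, the pooled SD is the right one. No opioid-use SD is given, and the later design is not specified.

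**Prior users may be excluded after all.** Text following the confounding-conditions criterion is redacted, so a limit on prior opioid use cannot be ruled out. The Visit 1 opioid side-effect assessment suggests that users are expected, but does not prove it.

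**These are descriptive secondary outcomes in a small single-arm series.** This stands. Section 8.1 names historical controls for BPI-5 pain, not for opioid outcomes, so no planned opioid comparison is biased. Any single-arm mean depends on case mix. The reason to single out this factor is that it is the pre-operative value of the outcomes themselves and is already scheduled.

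**Conclusion.** The point holds for the three opioid outcomes. As written, section 8.1 reports usage over intervals, time to cessation and side-effect counts without reference to pre-operative opioid use or symptoms, so the results mix prior status with postoperative need. It matters for interpreting secondary descriptive results, not for the primary pain endpoint.

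The size cannot be derived from the documents. Under the assumed ranges (10% to 40% prior users, usage ratio 1.5 to 3) the pooled mean is 5% to 80% above the non-user mean; at a ratio of 1 there is no shift. The mg figures rest on assumed doses and on unchanged continuation for 28 days. The conclusion further assumes that the redacted eligibility text does not exclude prior users. It makes no claim that the SD would be wrong for later planning.

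**What to change.** In section 8.1:
1. Report MED usage and time to opioid cessation by pre-operative opioid use (yes/no), beside the pooled figures. Take the status from Visit 1 or the first Visit 2, before lead placement; section 6.5.9 allows later repeats of Visit 2, and diary days under pre-operative stimulation are already on treatment.
2. Compute change in MED against that Visit 1/2 level where it is available, and state for how many subjects it is.
3. Treat subjects still using opioids at last follow-up as censored, and summarise time to cessation accordingly (for example Kaplan-Meier) instead of by a simple mean of days.
4. Report side effects absent at the pre-operative assessment separately from those already present. Presence or absence is enough, so no severity grading is needed.

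In sections 6.5.1 and 6.5.2, make the analgesic-use and opioid side-effect items ones that *will* be assessed, and reconcile the diary statement in section 3.3 with the optional diary in section 6.5.2.

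**Cost:** a few lines of analysis text and a firmer requirement on items already scheduled, with no change to clinical management. The downside is that the prior-user group will be small (0.15 × 36 ≈ 5 to 0.35 × 36 ≈ 13 subjects at assumed shares of 15% to 35%), so its estimates will be imprecise and should be presented as descriptive.
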